1.3 Schedule of Activities

Study assessments to be performed are outlined in [Table 1](#). If the Coronavirus Disease 2019 (COVID-19) pandemic prevents participants from coming to the site, participants can have their study visit assessments performed remotely as judged appropriate by the investigator. This must be discussed with the sponsor before being implemented. In such a case, the investigator will perform a telemedicine visit and will make every effort, where applicable, to contact the participant's general practitioner or specialist physician to ensure all important medical

information and safety event(s) occurring since the last visit are collected. Guidance on how to collect protocol-planned assessments is provided in Appendix 10.5. Such document will be filed in the trial master file.

Table 1 Schedule of Activities

Procedure	Screening (up to 28 days before Day 1)	Intervention Period												EoS/ ED	Section for further details
		-	-	Week 1	Week 1	Week 4	Week 12	Week 20	Week 24	Week 25	Week 25	Week 36	Week 44		
End of week	-	-													
Day [a]	Day -28 to Day -1	Day 1	Day 3	Day 7	Day 29	Day 85	Day 141	Day 169	Day 171	Day 175	Day 253	Day 309	Day 337		
Visit window			Day 3 after first inj	Day 7 after first inj	±3 days	±3 days	±3 days	±3 days	Day 3 after last inj	Day 7 after last inj	±3 days	±3 days	±3 days		
Informed consent	X														10.1.3
Inclusion and exclusion criteria	X														5.1 & 5.2
Demography	X														
Full physical examination including body weight	X [b]	X							X					X	8.3.1
Medical and surgical history	X														
Prior disease-specific treatment	X														
Electrocardiogram [c]	X													X	8.3.3
Vital signs	X	X			X	X	X	X			X	X	X		8.3.2
Imaging scan [e]	X														8.3.4
ECOG score	X													X	10.4
Injection triptorelin 6M		X							X						6.1
Blood samples for testosterone	X [d]	X [d]	X	X	X	X	X	X [d]	X	X	X	X	X	X	8.2
Blood samples for PSA		X						X						X	8.2
Blood samples for laboratory safety tests [f]	X													X	8.3.5
Local tolerance [g]		X						X							8.3.6

Procedure	Screening (up to 28 days before Day 1)	Intervention Period											EoS/ ED	Section for further details
		-	-	Week 1	Week 1	Week 4	Week 12	Week 20	Week 24	Week 25	Week 25	Week 36	Week 44	
End of week	-	-	Week 1	Week 1	Week 4	Week 12	Week 20	Week 24	Week 25	Week 25	Week 36	Week 44	Week 48	
Day [a]	Day -28 to Day -1	Day 1	Day 3	Day 7	Day 29	Day 85	Day 141	Day 169	Day 171	Day 175	Day 253	Day 309	Day 337	

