
 To demonstrate the effect of triptorelin embonate 22.5 mg 6-month formulation administered subcutaneously to suppress the 'acute-on-chronic' effect following the administration of the second dose 	
 Percentage of participants castrated on Day 3 and Day 7 after each injection administered on Day 1 and Day 169 (castration defined as testosterone <1.735 nmol/L (50 ng/dL))

 To demonstrate the effect of triptorelin embonate 22.5 mg 6-month formulation administered subcutaneously in the maintenance of PSA 	
 Percent change in PSA from baseline (prior to injection) at Day 169 and Day 337 (Percent change in PSA defined as the absolute value of difference between the PSA values at Day 169 and Day 337 and the baseline value divided by the baseline value)

Associated Procedure / Instruction Reference	319480-SOP
Form Reference	080091-FOR v7.0

Objectives	Endpoints

 To demonstrate the safety profile of triptorelin embonate 22.5mg 6-month formulation administered subcutaneously 	
 Incidence of TEAEs (including local tolerability) throughout the study i.e. up to Day 337 Change from baseline in clinical safety laboratory parameters (blood chemistry and haematology) at Day 337 Change from baseline in physical examination at Day 169 and Day 337 Change from baseline in ECG at Day 337 Change from baseline in vital signs (blood pressure and heart rate) at each visit up to Day 337

AE=adverse event; ECG=electrocardiogram; PSA=prostate-specific antigen; TEAE=treatment-emergent adverse event

Note: A list of laboratory parameters to be assessed during the study are presented in Protocol Appendix 10.2.

- Hypotheses**

Hypotheses for this study are defined below.

The primary objective of this study is to evaluate the efficacy triptorelin embonate 22.5 mg (6-month formulation) administered subcutaneously in maintaining serum testosterone castrate levels during the study (maintenance of castration defined as testosterone <1.735 nmol/L (50 ng/dL) at Day 29, Day 85, Day 141, Day 169, Day 253, Day 309 and Day 337) with two complete study intervention administrations. Thus, the null hypothesis to be tested is as follows:

Null hypothesis: percentage of participants castrated (serum level of testosterone <1.735 nmol/L) from date of first dose to Day 337 is less than or equal to 90%.

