2.2 Overall Study Design and Investigational Plan

This is a phase III, multicentre, open-label, non-comparative, repeat dose study to evaluate the efficacy and safety of triptorelin 6-month formulation (22.5 mg) administered subcutaneously in participants with locally advanced and/or metastatic prostate cancer previously treated and castrated with a GnRH analogue.

Approximately 145 participants will be assigned to triptorelin embonate 22.5 mg (6-month formulation) to be administered on Day 1 and Day 169. Note: participants must receive study intervention on Day 1 in accordance with the treatment schedule of their previously received GnRH analogue therapy.

[figure not shown]
The study will consist of a 4-week screening period, during which participants with prostate cancer will be screened for eligibility. On Day 1, all eligible participants will receive a single open-label administration of study intervention. Following treatment on Day 1, visits will occur on Day 3, Day 7, Day 29, Day 85, Day 141, Day 169 (second administration), Day 171, Day 175, Day 253, Day 309 and Day 337. (Note: if necessary, participants can request home visits, except for visits where study intervention is to be administered).

Participants will be considered to have completed the study when final procedures and assessments have been performed at the Day 337 visit. Participants who withdraw from the study before the completion of the Day 337 visit will have early discontinuation procedures and assessments performed at their final visit.

Associated Procedure / Instruction Reference	319480-SOP
Form Reference	080091-FOR v7.0

The study design is illustrated in [Figure 1](#).

Figure 1 Study Schema

D=day; ED=early discontinuation; EoS=end of study

Participants will receive a subcutaneous injection of triptorelin embonate 22.5 mg (6-month formulation) on Day 1 and Day 169.

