5.1.1 Outputs Presentation

5.1.1.1 Presentation of Visits / Timepoints

For by-visit summaries, the nominal visit as collected in the Electronic Case Report Form (eCRF) will be used in general for analysis purpose unless stated otherwise. Analysis visit window described in Section 6.1 will be used for slotting actual testosterone and prostate-specific antigen (PSA) assessment dates into planned schedule. Unscheduled visits will not be displayed in summaries but will be listed.

Visits in the TFLs will be presented as follows and in the following order:

Period	Long Visit Name	Short Name	Protocol Time Interval
Screening	Day -28 to Day – 1 (Screening)	Scr	
Intervention Period	Day 1 (Baseline)	Bsl	
	Week 1 – Day 3	D3	Day 3 after first injection
	Week 1 – Day 7	D7	Day 7 after first injection
	Week 4 – Day 29	D29	±3 day
	Week 12 – Day 85	D85	±3 day
	Week 20 – Day 141	D141	±3 day
	Week 24 – Day 169	D169	±3 day
	Week 25 – Day 171	D171	Day 3 after last injection
	Week 25 – Day 175	D175	Day 7 after last injection
	Week 36 – Day 253	D253	±3 day
EoS/ED	Week 44 – Day 309	D309	±3 day
	Week 48 – Day 337	D337	±3 day

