5.1.2 Descriptive Statistics

Due to the single-arm nature of the study, all statistical analyses will be descriptive. All raw and derived variables will be listed and described using summary statistics. For categorical variables, summary statistics will be displayed using descriptive statistics by frequency count and percentages by category. The missing category will be presented if applicable. Unless otherwise specified, participants with missing data will be included in the calculation of percentages. For quantitative variables, summary statistics will be displayed using descriptive statistics by number of observations, mean, standard deviation (SD), first quartile, median, third quartile, minimum and maximum. Frequency and proportion of missing data will be displayed.

Associated Procedure / Instruction Reference	319480-SOP
Form Reference	080091-FOR v7.0

For the efficacy analyses, the descriptive statistics of treatment effects and corresponding 95% CIs for the primary endpoint and secondary endpoints will be presented if applicable.

5.1.3 *Baseline Value*

Unless otherwise specified, baseline is defined as the last non-missing measurement taken prior to first Investigational Medicinal Product (IMP) administration (including unscheduled assessments).

5.1.4 *Reference Start Date and Study Day*

Reference start date is defined as the day of the first IMP administration.

The day of the first IMP administration will be Day 1. Study day will be calculated as:

- The difference between the event date and the reference date plus one day, if the event is on or after the reference date.
- The difference between the event date and the reference date, if the date of event is prior to the reference date.

Study day will appear in any listings where an assessment date or event date appears.

In case of partial or missing event date, study day will appear missing while any associated durations will be presented based on the imputations described in [Appendix 2](#).

5.2 **Enrolment, Disposition and Analysis Sets**

A Listing presenting study treatment dispensation details will be provided (Listing 16.1.7).

Following disposition summaries will be provided:

- Summary table with the number and percentage of participants screened, screen failed, reason for screen failures, enrolled, treated, having completed the study, withdrawn and reason for withdrawal,
- Summary table with the number and percentage of participants enrolled per visit,

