5.7.3 Analysis of Key Secondary Efficacy Endpoints

5.7.3.1 Secondary Efficacy Endpoints

The secondary efficacy endpoints are listed below:

- Percentage of participants castrated at each timepoint on Day 29, Day 85, Day 141, Day 169, Day 253, Day 309 and Day 337 (castration defined as testosterone <1.735 nmol/L (50 ng/dL))
- Percentage of participants with a serum testosterone level <0.694 nmol/L (20 ng/dL) during the study
- Percentage of participants with a serum testosterone level <0.69 nmol/L (20 ng/dL) at each timepoint on Day 29, Day 85, Day 141, Day 169, Day 253, Day 309 and Day 337
- Percentage of participants castrated on Day 3 and Day 7 after each injection administered on Day 1 and Day 169 (castration defined as testosterone <1.735 nmol/L (50 ng/dL))
- Percent change in PSA from baseline (prior to injection) at Day 169 and Day 337 (Percent change in PSA defined as the absolute value of difference between the PSA values at Day 169 and Day 337 and the baseline value divided by the baseline value).

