6 DATA HANDLING

6.1 Visit window

The time window for visit/timepoints will be applied as below for the blood samples for testosterone. In case of multiple unscheduled and planned visits enclosing within the defined analysis time interval, the non-missing value in a visit closest to the target visit day will be used in the summary tables.

Study phase	Scheduled visit	Protocol Time Interval	Analysis Time Interval* (days)
Screening	Day -28 to Day -1		-28 to -1
Intervention Period			
	Day 1 (first injection)	<1	<=1
	Week 1 – Day 3	3	2 to 5
	Week 1 – Day 7	7	6 to 18
	Week 4 – Day 29	29	19 to 57
	Week 12 – Day 85	85	58 to 113
	Week 20 – Day 141	141	114 to 155
	Week 24 – Day 169 (second injection)	169 (D2)	156 to D2
	Week 25 – Day 171	171 (D2+2)	D2+1 to D2+4
	Week 25 – Day 175	175 (D2+6)	D2+5 to D2+45
	Week 36 – Day 253	253 (D2+84)	D2+46 to D2+112
	Week 44 – Day 309	309 (D2+140)	D2+113 to D2+154
End of Study/Early Discontinuation	Week 48 – Day 337	337 (D2+168)	≥D2+155

*Analysis visit window after screening are defined using the mid-point between each scheduled visit and reset with the second injection.

6.2 Unscheduled Visits, Retest, Withdrawal Visit,

All listings will include retest measurement and assessments from unscheduled visits. For by-visit summary, only planned visits in the protocol will be presented.

Assessments from unscheduled visit and retest measurements will be included for baseline value determination whenever applicable. These measurements will also be used to determine worst toxicity grade for laboratory data, or meeting PCSA criteria in vital signs or ECG.

If an assessment requires a retest (for example, safety laboratory, vital signs and ECG), the closest non-missing value to the scheduled visit will be used in the summary tables.

Participants who have withdrawn early from the study have their last assessment entered at the end of study / early discontinuation visit in the eCRF.

Associated Procedure / Instruction Reference	319480-SOP
Form Reference	080091-FOR v7.0

IPSEN GROUP

CONFIDENTIAL

D-FR-52014-245

SAP Final: Version 1.0: 30 January 2023

PAGE 26/43

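### SAP 6.1 lets a sample taken up to 45 days after the second injection stand as its Day 7 result, against 17 days after the first

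*SAP*

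**What the plan says.** The secondary endpoint in SAP 5.7.3.1 is "Percentage of participants castrated on Day 3 and Day 7 after each injection administered on Day 1 and Day 169". The objective behind it, in SAP 2.1, is "to suppress the 'acute-on-chronic' effect following the administration of the second dose".

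The protocol's Schedule of Activities (section 1.3) fixes the second-dose sample at "Day 7 after last inj" with no tolerance. The visits from Day 29 onward, other than Days 171 and 175, have ±3 days.

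For analysis, SAP 5.1.1.1 says that the windows in section 6.1 "will be used for slotting actual testosterone and prostate-specific antigen (PSA) assessment dates into planned schedule". The footnote to the window table gives the rule: "Analysis visit window after screening are defined using the mid-point between each scheduled visit and reset with the second injection". The table then sets:

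- Day 7: study Days 6 to 18
- Day 175: D2+5 to D2+45, where D2 is the day of the second injection

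If several planned and unscheduled values fall in one window, "the non-missing value in a visit closest to the target visit day will be used in the summary tables". The SAP gives no narrower window for the acute-on-chronic endpoint.

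**The concern.** Days 7 and 175 are meant to capture the same thing, testosterone about a week after an injection. The SAP collects them over very different spans, and the wider span falls on the dose that the objective is about.

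A castrate value from several weeks after the second injection could be reported as castration on Day 7. A loss of castration first seen at that time could be reported as a Day 7 failure. The by-visit table would show neither as a late sample.

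The FAS definition (SAP 4) does not prevent this. Its list of required testosterone visits omits Days 171 and 175, so a man without a timely Day 175 sample stays in the set.

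**Working it through.** **Inputs.**
- First-cycle visits (SAP 2.2): Days 3, 7, 29, 85, 141, 169.
- Second-cycle visits, as days after D2 (SAP 6.1): 2, 6, 84, 140, 168.
- Day numbering (SAP 5.1.4): "The day of the first IMP administration will be Day 1", so study Day d is d − 1 days after the first dose.

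**Reproducing the SAP's limits.**
- Day 7: lower mid-point (3 + 7)/2 = 5, so the window starts on Day 6. Upper mid-point (7 + 29)/2 = 18.
- Day 175: lower mid-point (2 + 6)/2 = 4, so the window starts at D2+5. Upper mid-point (6 + 84)/2 = 45.
- The remaining mid-points also match the table: 57, 113 and 155 in the first cycle; D2+112 and D2+154 in the second.

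The table follows its own rule. The asymmetry comes from the schedule. The gap to the next visit is 29 − 7 = 22 days in the first cycle and 84 − 6 = 78 days in the second, because no visit after the second dose corresponds to Day 29.

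**On the same scale, days after injection.**

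| | First injection (Day 7) | Second injection (Day 175) |
|---|---|---|
| Window | 6 − 1 = 5 to 18 − 1 = 17 | 5 to 45 |
| Width | 17 − 5 + 1 = 13 days | 45 − 5 + 1 = 41 days |
| Latest sample past target (+6) | 17 − 6 = 11 days | 45 − 6 = 39 days |

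The ratio of widths is 41/13 = 3.2. The stretch D2+18 to D2+45 has 45 − 18 + 1 = 28 days, or 28/41 = 68% of the Day 175 window. The same offsets after the first injection are study Days 19 to 46, all inside the Day 29 window (19 to 57).

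**What is not affected.** The Day 3 window (study Days 2 to 5) and the Day 171 window (D2+1 to D2+4) are both 1 to 4 days after injection. Day 175 is not one of the seven primary timepoints.

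**How a late value could enter.**
- *Late Day 175 visit.* Protocol 7.3 tells sites to rebook missed visits promptly. A visit more than 11 days late would still be slotted to Day 175.
- *Unscheduled or repeat sample.* Protocol 8 allows these for safety or technical reasons. SAP 6.1 lets them compete for a window, while SAP 5.1.1.1 and 6.2 keep unscheduled visits out of summaries. The passages conflict.
- *On-schedule Day 253 sample.* This cannot enter. With D2 on Day 169 it falls at D2+81 at the earliest (84 − 3).

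**Weight of one man.** If the FAS has the 130 participants assumed in the sample size, each such man carries 1/130 = 0.8 percentage points of the Day 175 rate.

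**The case against.** The strongest reply is that this will rarely happen. The closest-value rule admits a late sample only when nothing nearer to D2+6 lies in the window. No scheduled visit falls between D2+18 and D2+45. The unscheduled route is ambiguous. What clearly remains is a Day 175 visit more than 11 days late in a man who otherwise qualifies for the FAS. In addition, efficacy is descriptive (SAP 5.7.1.1) and no comparison between the two injections is planned. All of this stands, and it limits the point to a minor one.

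Four stronger readings are tempting, and the documents do not support them:

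- *Early-discontinuation samples inflate the rate.* This route is mostly closed. The FAS requires the later visits unless a value is at or above 50 ng/dL, and intercurrent event 1 (SAP 5.7.2.1) sets aside men who leave without such a value.
- *A late sample falls after any surge and says nothing about it.* Neither document states how long a surge lasts. The argument rests only on the endpoint's own Day 3 and Day 7 timing.
- *A definite share of the Day 175 rate is wrong.* The documents give no basis for a count of affected men.
- *The windows are miscalculated.* They reproduce exactly.

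It can also be said that D2+17 is no more surge-based than D2+45, since it still accepts a sample 11 days past target. That is fair. Its merit is that both injections are then measured on the same basis. It is also the limit that the SAP's own rule would give if a visit existed at D2+28: (6 + 28)/2 = 17.

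**Conclusion.** The concern holds as a minor point about one secondary result. Applied to an uneven schedule, the mid-point rule lets a sample up to 39 days past target stand as the Day 7 result after the second injection. After the first injection the limit is 11 days past target, and later samples go to Day 29. Nothing elsewhere in the SAP narrows this for the endpoint.

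The conclusion rests on the window table as written, on slotting by actual date, and on the FAS list omitting Day 175. The number of men affected is unknown and may be zero. The weight of 0.8 percentage points per man assumes a FAS of 130.

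**What to change.** In SAP 6.1, end the Day 175 window at D2+17, which matches the first-injection Day 7 window. List values from D2+18 to D2+45 without assigning them to a by-visit cell. They remain available for the FAS note on values at or above 50 ng/dL and for Primary-S3, which uses no window. The Day 253 window still starts at D2+46, so the primary windows do not change.

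Three clarifications should go with it:

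- **Denominator.** State that the Day 171 and Day 175 percentages use participants with a value in the window, with the number missing shown. Otherwise SAP 5.1.2 and Appendix 3 keep men with missing values in the denominator, in effect counting them as not castrated.
- **Unscheduled samples.** Reconcile 6.1 with 5.1.1.1 and 6.2.
- **Missing-value rules.** State that intercurrent event 2 and its Primary-S1 version refer to the seven primary days. Intercurrent event 2 speaks of any planned testosterone measurement, so a Day 175 value made missing by the narrower window could otherwise be read as affecting the primary analysis.

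The cost is one table cell and a few sentences. The downside is that a few Day 175 values may become missing.

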Visit window			Day 3 after first inj	Day 7 after first inj	±3 days	±3 days	±3 days	±3 days	Day 3 after last inj	Day 7 after last inj	±3 days	±3 days	±3 days	
Previous (excluding disease-specific) and concomitant medication	X	X	X	X	X	X	X	X	X	X	X	X	X	6.8
Adverse events	X	X	X	X	X	X	X	X	X	X	X	X	X	8.4

Abbreviations: 6M=6-month formulation; AE=adverse event; ALT=alanine aminotransaminase; AST=aspartate aminotransaminase; eCRF=electronic case report form; ECG=electrocardiogram; ECOG= Eastern Cooperative Oncology Group; EoS=end of study; Hb=haemoglobin, inj=injection; M=month; PSA=prostate-specific antigen WBC=white blood cell

- a If necessary, participants can request home visits, except for visits where study intervention is to be administered.
- b Height to be collected at screening only.
- c ECG to be assessed as clinically indicated at any other time during the study as required.
- d All testosterone assessments to be performed using the central laboratory, except at screening. At screening, testosterone to be assessed up to 7 days prior to Day 1 using the local laboratory. On Day 1 and Day 169, samples for testosterone to be collected pre-dose.
- e An imaging scan is not required if performed within 6 months of study screening.
- f Haematology (WBC and differential count, platelet count, Hb), blood chemistry (creatinine, glucose, ALT, AST, alkaline phosphatase, total and conjugated bilirubin). Glucose: Non-fasting levels in all participants.
- g Injection site to be specifically checked for local site injection reactions 2 hours after study intervention administration. Any local reaction AEs will be collected on the eCRF.

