8 STUDY ASSESSMENTS AND PROCEDURES

- Study procedures and their timing are summarised in the SoA. Protocol waivers and exemptions are not allowed.
- Adherence to the study design requirements, including those specified in the SoA, is essential and required for study conduct.
- All screening evaluations must be completed and reviewed to confirm that potential participants meet all eligibility criteria. The investigator will maintain a screening log to record details of all participants screened and to confirm eligibility or record reasons for screening failure, as applicable.
- Procedures conducted as part of the participant's routine clinical management (e.g. blood count) and obtained before signing of the ICF may be utilised for screening or baseline purposes provided the procedures met the protocol-specified criteria and were performed within the timeframe defined in the SoA (Table 1).
- In the event of a significant study-continuity issue (e.g. caused by a pandemic), alternate strategies for participant visits, assessments, medication distribution and monitoring may be implemented by the sponsor or the investigator, as per local health authority/ethics requirements.
- The maximum amount of blood for study purposes collected from each participant over the duration of the study will not exceed 153 mL.
- Repeat or unscheduled samples may be taken for safety reasons or in case of technical issues with the samples.

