5.7.2 Analysis of Primary Efficacy Endpoint

5.7.2.1 Primary Efficacy Endpoint, Treatment Effect and Estimand Definition

To assess the primary objective, the primary estimand will be defined by the following attributes:

- Population: participants with locally advanced and/or metastatic prostate cancer previously treated and castrated with a GnRH analogue as defined by the listed Inclusion/Exclusion criteria in sections 5.1 and 5.2 of the protocol, respectively.
- Variable/Endpoint: castration maintenance rate during the study defined as percentage of participants castrated (testosterone < 1.735 nmol/L (50 ng/dL)) at Day 29, Day 85, Day 141, Day 169, Day 253, Day 309 and Day 337, with two complete study intervention administrations.
- Key Intercurrent event (ICE):
 - (a) ICE 1 - Subjects discontinued from study prior to Day 337 without evidence of inadequate testosterone suppression (testosterone measurement \geq 50 ng/dL)
The testosterone values of these participants will not be considered for the main analysis (principal stratum strategy).
 - (b) ICE 2 - Subjects with at least one planned testosterone measurement missing on or prior to Day 337 without evidence of inadequate testosterone suppression (testosterone measurement \geq 50 ng/dL)
The testosterone values of these participants will not be considered for the main analysis (principal stratum strategy).

Associated Procedure / Instruction Reference	319480-SOP
Form Reference	080091-FOR v7.0

(c) ICE 3 - Subjects discontinued treatment prior to receiving the second study intervention administration without evidence of inadequate testosterone suppression (testosterone measurement ≥ 50 ng/dL)
The testosterone values of these participants will not be considered for the main analysis (principal stratum strategy).

(d) ICE 4 - Subjects received a prohibited medication during the study
Prohibited medication with impacts on the testosterone value will be identified through blinded data review. Subjects receiving identified prohibited medication (for example, finasteride, dustasteride, or abiraterone) will be included in the primary analysis as non-responder. In contrast, all testosterone measurements from subjects receiving prohibited medications other than identified ones during the study will be included in the primary analysis (composite strategy).

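### Protocol Table 1 and SAP 6.1 count the last three primary visits from different injections, so after a second injection 14 or more days late the Day 337 analysis window can be empty for a man who attended every visit

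*SAP*

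**What the plan says.** **Schedule.** SAP 5.1.4 (Reference Start Date and Study Day) fixes the clock: "The day of the first IMP administration will be Day 1". In the visit-window row of Protocol Table 1, Days 171 and 175 are tied to the second injection (for Day 175, "Day 7 after last inj"), but Days 253, 309 and 337 carry only ±3 days. Protocol 8 adds: "Adherence to the study design requirements, including those specified in the SoA, is essential and required for study conduct". No sentence moves the three later visits when the second injection is late.

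**Late dosing.** Day 169 has a ±3-day window. Protocol 7.1.1 allows postponement in a government-declared emergency. Protocol 10.5.1.4 places men with confirmed COVID-19 on immediate delay; it also says that delayed dosing visits are not allowed under the protocol and must be escalated to the sponsor. Neither section limits the delay or reschedules later visits.

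**Analysis.** SAP 5.1.1.1 states: "Analysis visit window described in Section 6.1 will be used for slotting actual testosterone" and PSA dates into the planned schedule. The footnote to the SAP 6.1 table gives the rule: "Analysis visit window after screening are defined using the mid-point between each scheduled visit and reset with the second injection". In SAP 6.1 the Day 309 window is "D2+113 to D2+154" and the Day 337 window opens at D2+155. Where several values share a window, "the non-missing value in a visit closest to the target visit day will be used in the summary tables".

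**Primary analysis.** ICE 2 in SAP 5.7.2.1 covers "Subjects with at least one planned testosterone measurement missing on or prior to Day 337 without evidence of inadequate testosterone suppression"; these men are left out of the main analysis. The FAS definition in SAP 4 asks for two injections and completion of the testosterone visits. Its note also keeps any man with a measurement of 50 ng/dL or more.

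**The concern.** The primary endpoint needs a castrate value at each of seven days, the last being Day 337. A site that follows Table 1 after a late second injection takes the last sample on Day 337, while the SAP looks for it at D2+155 or later. Beyond a certain delay these do not meet, and the man has no Day 337 value although he missed nothing.

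Three things follow.

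- **The denominator becomes ambiguous.** ICE 2, read by analysis window, removes him; the FAS definition, read by visit, keeps him.
- **Any exclusion is one-sided.** The FAS note retains men with a value of 50 ng/dL or more, so only castrated men can be lost this way, which lowers the observed rate.
- **The second dose is tested for less than its interval.** A last sample on Day 337 comes fewer than 168 days after a late second dose.

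The sensitivity analyses treat him differently. S1 applies the window but keeps a man with a single missing value. S2 and S3 do not apply it. Part of any gap between primary and sensitivity results could then come from slotting alone.

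**Working it through.** **1. The plan's own figures.** With scheduled offsets of 84, 140 and 168 days after D2 (SAP 6.1), the mid-points are (84+140)/2 = 112 and (140+168)/2 = 154. The Day 309 window is therefore D2+113 to D2+154 and Day 337 starts at D2+155, as printed. For the sample size (SAP 2.3: 90% null rate, 97% alternative, n = 130), success needs at most 6 failures. The one-sided error is P(X ≥ 124 | 130, 0.90) = 0.0207 and power is P(F ≤ 6 | 130, 0.03) = 0.9027. Dropout: 130/0.90 = 144.4, giving 145. All reproduce.

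**2. Threshold.** Let the second injection be d days late, so D2 = Day 169+d. A sample on Day s is then D2 + (s − 169 − d), and it stays in the Day 337 window only if s − 169 − d ≥ 155.

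| Last sample | Offset from D2 | Stays in window if | Leaves it from |
|---|---|---|---|
| Day 334 | 165 − d | d ≤ 10 | 11 days late |
| Day 337 | 168 − d | d ≤ 13 | 14 days late |
| Day 340 | 171 − d | d ≤ 16 | 17 days late |

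A Day 337 sample lands in the Day 309 window while 168 − d ≥ 113, that is, for delays of 14 to 55 days. From 56 days it lands in the Day 253 window, and Days 309 and 337 are both empty. These are two consecutive missing values, which S1 counts as non-response.

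**3. Example: D2 on Day 190 (21 days late), Table 1 days kept.**

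| Sample | Offset from D2 | Window | Distance to Day 309 target (D2+140) |
|---|---|---|---|
| Day 253 | 253 − 190 = 63 | Day 253 | – |
| Day 309 | 309 − 190 = 119 | Day 309 | 21 |
| Day 337 | 337 − 190 = 147 | Day 309 | 7 |

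The Day 337 sample is nearer the target, so it becomes the Day 309 value. The real Day 309 value is unused and Day 337 is empty. The last sample is 147 days after the second dose, not 168. At exactly 14 days late the two samples tie (14 days each), and SAP 6.1 gives no tie rule.

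**4. Visits moved with the injection.** Samples at D2+84, D2+140 and D2+168 are the window targets themselves, so all three windows are filled whatever the delay.

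**5. Size.** Exact (Clopper-Pearson) 95% lower bound, which must exceed 90%:

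| Evaluable men | Failures | Lower bound | Success |
|---|---|---|---|
| 130 | 6 | 90.23% | yes |
| 130 | 7 | 89.22% | no |
| 129 | 6 | 90.15% | yes |
| 128 | 6 | 90.08% | yes |
| 127 | 6 | 90.001% | yes |
| 126 | 6 | 89.92% | no |

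Losing 1 to 3 castrated men leaves the limit at 6 failures. Losing 4 (4/130 = 3.1%) lowers it to 5. Power at a true 97% is then P(F ≤ 5 | 130, 0.03) = 0.803 if failures arise among all 130 men, or P(F ≤ 5 | 126, 0.03) = 0.821 if only among the other 126.

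**The case against.** **Late dosing is exceptional.** A delay of 14 days is far outside the ±3 days for Day 169. Protocol 10.5.1.4 does not permit such delays and sends each to the sponsor, and 7.1.1 is confined to declared emergencies. This stands, and it keeps the point minor.

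**The SAP shows the intended schedule.** In the column for the protocol's interval, SAP 6.1 prints D2+84, D2+140 and D2+168 beside Days 253, 309 and 337, so its authors seem to have expected visits to move. That is likely, and the windows then work. But no instruction to sites says so, and moving a visit by more than 3 days departs from Table 1.

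**ICE 2 is about missing measurements, not empty windows.** A man sampled on every Table 1 day has had each planned measurement. This reading is open, so exclusion is not certain. Against it, SAP 5.1.1.1 slots testosterone by window, Protocol 3 lists analyses without the visit window as secondary estimands, and S1 and S2 differ in whether the window applies. All three suggest that the primary analysis uses it.

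**Any effect would be visible.** S2, S3 and the by-subject listings would show it. True, but only after the data are known, in an open-label trial.

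**A stronger reading.** A reader might infer that a displaced Day 309 value of 50 ng/dL or more disappears and turns 123/130 into 124/130. The documents do not support this. With Day 337 empty, the man cannot be castrated at all seven days, so he cannot enter the numerator. The FAS note keeps him on the strength of the measurement, and he counts as a failure: 123/130. Removing him (123/129, lower bound 90.15%) would require counting only slotted values as evidence of escape, a limit that neither the FAS note nor ICE 2 states.

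**Conclusion.** The mismatch between the two clocks is real and the 14-day threshold is exact for a sample on Day 337. The consequence is conditional: the second injection must be late enough, the site must keep the Table 1 days, and missing in ICE 2 must be read by analysis window. A castrated man with complete sampling is then left out of the primary analysis. Even if he is kept, his last sample does not test the end of the second dosing interval.

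The size is small. The documents give no frequency of late dosing; with no second injection 11 or more days late there is no effect. One to three such men do not change success with 6 failures. Four or more would be needed to lower the limit to 5 failures and power to 80-82%. That starts from 130 evaluable men after all other losses; the allowance of 145 − 130 = 15 men could absorb some of them. Minor severity: a cross-document gap worth closing, not a threat to the trial's conclusion.

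**What to change.** 1. **Protocol Table 1, 7.1.1 and 10.5.1.4:** state that if the second injection is postponed, the Day 253, Day 309 and Day 337 visits are held 84, 140 and 168 days (±3 days) after it. This matches SAP 6.1 and covers the full second dosing interval.
2. **SAP 6.1:** for men with D2 after Day 172 (169+3) who were already sampled on the original days, assign those samples to the nominal visit in the eCRF, so that slotting alone does not trigger ICE 2. Flag any man whose last sample is earlier than D2+155, because counting it as Day 337 does not make it an end-of-interval value.

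A general rule keeping every late-dosed man in the FAS is not advised: it could override ICE 1 and ICE 2 for a man who later withdraws or really misses a sample.

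**Cost.** A small protocol amendment, which needs ethics committee approval (Protocol 10.1.1) in a trial run in seven countries (SAP 5.7.1.3), and a short SAP addition before database lock. Last visits for late-dosed men move by the length of the delay. No extra participants or samples.
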